14.1 Definitions

Adverse Event (AE) is any untoward medical occurrence, unintended disease or injury or untoward clinical sign (including abnormal laboratory findings) in subjects, users or other persons, whether or not related to the investigational medical device.

For study subjects this definition includes events related to the procedures involved, as well
pregnancy in females.

 For users or other persons this definition is restricted to events related to the investigational medical device.

Adverse Device Effect (ADE): is an AE related to the use of the investigational medical device.

 This includes any AE resulting from insufficiencies or inadequacies in the instructions for use, the deployment, the implantation, the installation, the operation, or any malfunction of the investigational medical device. In addition, this includes any event that is a result of a use error or intentional misuse.

Serious Adverse Event (SAE) is an AE that led to any of the following conditions:

- Death;
 - Serious deterioration in the health of the subject that either resulted in:
 - A life-threatening illness or injury, or
 - A permanent impairment of a body structure or a body function, or
 - o In-subject hospitalization or prolonged hospitalization, or
 - Medical or surgical intervention to prevent life-threatening illness or injury or permanent impairment to a body structure or a body function, or
 - o Malignant tumour;
- Foetal distress, foetal death, a congenital abnormality or birth defect.

A planned hospitalization for pre-existing condition, or a procedure required by the CIP, without a serious deterioration in health, is not considered to be an SAE.

Serious Adverse Device Effect (SADE) is an ADE that has resulted in any of the consequences characteristic of an SAE.

Unanticipated Serious Adverse Device Effect (USADE) is defined as an SADE which by its nature, incidence, severity or outcome has not been identified in the current version of the investigator's Brochure.

Device deficiency is any inadequacy of a medical device with respect to its identity, quality, durability, reliability, safety or performance. This may include malfunctions, use errors, and inadequate labelling.

Device deficiency that might have led to an SAE if a) suitable action had not been taken, or b) intervention had not been made, or c) if circumstances had been less fortunate, is classified as a special type of deficiency and is handled under the SAE reporting system.

14.2 Method of detecting AEs

AEs will be detected at each visit by clinical examination and by asking the subject about the occurrence of AEs. Care should be taken not to introduce bias when eliciting AE information from the subject. Open-ended and non-leading verbal questioning is the preferred method and appropriate questions include:

- *"How are you feeling?"*
- "Have you had any medical problems since your last visit/contact?"
- "Have you taken any new medication since your last visit/contact?"

In addition, the subjects will be instructed to immediately contact the investigator/study site in case of occurrence of any untoward event between visits.

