NLF-SRS grading of nasolabial folds⁰	X**		x	x	х
Urine pregnancy test ^d	X**				
Eligibility assessment	X**				
Treatment	Х	X§			
Photography	X**	X§	Х	х	Х
Pain assessment ^e	Х	xΩ			
GAIS assessment ^f			х	х	Х
Subject satisfaction ^g			Х	х	Х
Adverse events ^h	x***	Х	x	х	Х
Concomitant medication ^h	x***	х	х	х	х

* Includes screening and treatment.

** Prior to application of the investigational device

*** From beginning of the treatment onwards

- § Optional, to be done at investigator's discretion
- Ω To be performed only if Touch-up treatment occurred
- ^a Includes date of birth, sex, and race
- ^b All medication taken by the subject within the previous 10 days
- Performed by the investigator using the Nasolabial Folds Severity Rating Scale (NLF-SRS); the severity of the left and the right fold will be separately graded
- ^d In females of child-bearing potential only, including women who are postmenopausal for less than 12 months
- Evaluated by the subject immediately after injection and approximately 15 min. thereafter using an 11-point Numeric Pain Rating Scale
- ^f Evaluated by the investigator using the Global Aesthetic Improvement Scale (GAIS)
- ^g Evaluated by the subject
- ^h To be collected throughout the investigation, from beginning of the treatment until the last visit

List of abbreviations

ADE	Adverse device effect
AE	Adverse event
BDDE	1,4-butanediol diglycidyl ether
CIP	Clinical investigation plan
CRF	Case report form
DCF	Data clarification form
EC	Ethics Committee
eCRF	Electronic Case report form
GAIS	Global Aesthetic Improvement Scale
GCP	Good clinical practice
HA	Hyaluronic acid
IB	Investigator's brochure
ICF	Informed consent form
MedDRA	Medical Dictionary for Regulatory Activities
mIU	Milli-international unit
NLF	Nasolabial fold
NLF-SRS	Nasolabial Folds Severity Rating Scale
NPRS	Numeric Pain Rating Scale
PT	Preferred term
SADE	Serious adverse device effect
SAE	Serious adverse event
SAP	Statistical analysis plan
SOC	System organ class
TMF	Trial master file
USADE	Unanticipated serious adverse device effect
UV	Ultraviolet
w/w	Weight/weight

Table of contents

Арр	Approval and signature pages		
Syno	opsis	5	
Sche	edule of procedures and events	8	
List	of abbreviations	9	
1	Background	. 13	
2	Identification and description of the investigational device	. 13	
2.1	Device description	. 13	
2.2	Manufacturer	. 14	
2.3	Intended use and mode of administration	. 14	
2.4	Traceability	. 14	

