4.2 Anticipated adverse device effects

The safety profile of BDDE-cross-linked hyaluronic acid dermal fillers, with or without lidocaine, is well established. In general, these devices are well tolerated and safe, with a low frequency of side effects¹⁷. Adverse effects that have been observed with devices similar to Princess[®] VOLUME Lidocaine are summarized in Table 2, on the following page.

Currently, there are no human safety data on Princess[®] VOLUME Lidocaine. There is, however, a considerable experience with Princess[®] VOLUME, which is essentially the same device, just without lidocaine. Almost 2 million (1,971,500) units of Princess[®] VOLUME (without lidocaine) have been sold worldwide from 2009 up to the end of 2015, and during the same period there were only 38 spontaneous ADE reports. Among these, 22 were cases of oedema, redness, inflammation, pain or swelling, which are commonly observed with any dermal filler. The remaining 16 comprised cases of nodules, lumps, burning, discoloration and a single report of an allergic reaction, all of which resolved shortly after occurrence⁸.

Table 2. Adverse effects of cross-linked hyaluronic acid dermal fillers (with or without lidocaine)

Common	Rare	Very rare
 Redness, erythema Swelling, oedema Pain, itching, burning, discomfort Tenderness Bleeding Bruising, hematoma 	 Hypersensitivity, angioedema Infection, abscess Herpes reactivation Irritation, inflammation, granuloma Malar oedema Implant visibility, nodules, beading, lumpiness, implant-site mass Firmness, induration Discoloration, dispigmentation, puncture marks Paresthesia, numbness Implant migration Scar sarcoidosis Scleromyxedema Teleangiectasia (generalized) Vasculitis cutaneous Vasospasm Vasovagal reaction during injection 	 Vascular compromise or arterial occlusion (typically presented as immediate skin blanching, followed by a Livedoid pattern, discoloration or necrosis) Retinal artery occlusion, vision loss Necrosis

Common AEs like swelling, redness, tenderness, pain and bruising are typically mild in severity and usually resolve within 1-2 days after injection; resolution of bruising may take a little bit longer. Discomfort and pain may be reduced or prevented by application of ice before the injection or local anaesthesia. Redness, swelling and bruising may be prevented or alleviated by application of ice-packs for 5-10 minutes after the injection.

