6.1.3 Safety endpoints

The safety of the investigational device will be evaluated using the following endpoint:

• Occurrence and frequency of adverse events

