6.1.4.2 Week 2 Visit (Visit 2)

The following assessments will be performed 2 weeks (± 2 days) after Visit 1:

- Photography (Optional)
- Touch-up treatment (optional)
- Pain assessment (only if Touch-up treatment performed)
- Adverse events
- Concomitant medication

6.1.4.3 Week 4 (Visit 3), Week 24 (Visit 4) and Week 36 (Visit 5) Visits

The following assessments will be performed respectively 4 weeks (\pm 4 days), 24 weeks (\pm 7 days) and 36 weeks (\pm 7 days) after Visit 1:

- Photography
- NLF-SRS grading of nasolabial folds
- GAIS assessment
- Subject satisfaction
- Adverse events
- Concomitant medication

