6.4.10 Safety monitoring

The safety of the investigational device will be monitored throughout the investigation, from Day 0/visit 1 until the final visit (visit 5). AEs will be collected at each visit. In addition, the subjects will be instructed to immediately contact the investigator by phone in case of occurrence of any untoward event between the visits. The procedure for collection, recording and reporting of AEs is described in Section 14.

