
4.5 Safety Analysis

Adverse events (AEs)

AEs will be coded by using the Medical dictionary for regulatory activities (MedDRA) version 19.1.

AEs will be tabulated by system organ class (SOC) and preferred term (PT). The number of entries, as well as the number and rate of affected subjects will be reported.

Deaths, SAEs and AEs with a causal relationship to the investigational device or procedure (definite, probable, possible or missing relationship) and AEs by intensity (mild, moderate, severe) are presented separately. Listings of adverse events leading to treatment discontinuation and those identified as "severe" will be provided.

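### Reactions that usually last 1-2 days have no structured recording between the Day 0 check and day 12-16, so they are likely to be under-ascertained

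*Protocol*

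**What the plan says.** Protocol section 6.1.3 names one safety endpoint: "Occurrence and frequency of adverse events". SAP section 4.5 turns it into counts by system organ class and preferred term: "The number of entries, as well as the number and rate of affected subjects will be reported". It also calls for tables by intensity and by causal relationship.

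Protocol section 4.2 describes swelling, redness, tenderness, pain and bruising as common and typically mild. It says that they "usually resolve within 1-2 days after injection; resolution of bruising may take a little bit longer".

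Collection begins on the injection day. The Table 1 footnote for AEs at Visit 1 reads "From beginning of the treatment onwards", and section 6.1.4.1 lists AEs at the Baseline Visit after treatment and pain assessment. Section 6.2.2 asks the subject to remain for several minutes after injection. Section 6.4.7 has the subject rate pain immediately and about 15 minutes later, after a neutral opening question.

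For the next visit, section 6.1.4.2 states: "The following assessments will be performed 2 weeks (± 2 days) after Visit 1". Section 6.4.10 states: "AEs will be collected at each visit". Section 14.2 combines clinical examination with questioning and says of the questioning: "Open-ended and non-leading verbal questioning is the preferred method". Between visits, subjects are told to contact the site at once about any untoward event. Neither document describes a diary, a scheduled call or a list of expected reactions.

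**The concern.** The reactions the protocol expects most often are short. Once the subject leaves on Day 0, the period in which they develop and fade contains no scheduled contact and no prospective record. By Week 2 an examination cannot see a reaction that has already gone, and an open question picks it up only if the subject remembers it and thinks it worth mentioning. Section 14.3 nevertheless requires a start date, an end date where applicable, and the worst intensity reached. For a reaction that peaks at home, those entries would be reconstructed from memory.

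This matters because section 4.2 states that there are no human safety data on this device, so the trial supplies its first reaction rates. Section 7.1 claims robust estimation of safety parameters as well as performance, and section 3.3 says that information on the occurrence of pain will come mainly from AE collection. A low reported rate could reflect good tolerability or poor recall, and the data would not separate the two. How much is missed could also differ between sites, depending on how each one asks.

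**Working it through.** **1. The plan's own precision figure.** The half-width of a two-sided 95% interval for a proportion is 1.96 × √(p(1−p)/n). With p = 0.900:
- n = 60: 1.96 × √(0.09/60) = 0.0759. Protocol section 7.1 and the SAP give 0.076.
- n = 40: 1.96 × √(0.09/40) = 0.0930. The SAP gives 0.093.

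Both reproduce. They concern the Week 24 success rate. The documents state no precision for AE rates.

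**2. Scheduled gaps**, from the visit windows in Table 1 and section 6.1.4 (all counted from Visit 1):
- Week 2 ± 2 days is day 12 to 16, so the gap from Day 0 is 12-16 days.
- Week 4 ± 4 days is day 24 to 32. From a touch-up at Week 2, the shortest gap is 24 − 16 = 8 days and the longest is 32 − 12 = 20 days.
- A reaction to the first injection that ends on day 1-2 has been over for 12 − 2 = 10 to 16 − 1 = 15 days when Week 2 is reached.

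These figures measure the time to the next scheduled enquiry. They do not measure the number of missed events.

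**3. What covers each period:**

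| Period | Recording described |
|---|---|
| Injection to about 15 minutes | Examination, open question, two pain ratings |
| Departure to day 12-16 | Contact started by the subject only |
| Week 2 visit | Examination and questioning; for resolved reactions, recall |
| Touch-up departure to Week 4 (8-20 days) | Contact started by the subject only |

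**4. Illustration of size (assumption only).** Neither the true incidence p nor the captured fraction s is given in the documents. The observed rate is p × s and the bias is −(1 − s) × p. The last column is the 95% half-width around the observed rate at n = 60:

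| True p | Captured s | Observed | Bias | Half-width |
|---|---|---|---|---|
| 0.30 | 0.80 | 0.24 | −0.06 | 0.108 |
| 0.30 | 0.60 | 0.18 | −0.12 | 0.097 |
| 0.30 | 0.40 | 0.12 | −0.18 | 0.082 |
| 0.50 | 0.80 | 0.40 | −0.10 | 0.124 |
| 0.50 | 0.60 | 0.30 | −0.20 | 0.116 |
| 0.50 | 0.40 | 0.20 | −0.30 | 0.101 |
| 0.70 | 0.80 | 0.56 | −0.14 | 0.126 |
| 0.70 | 0.60 | 0.42 | −0.28 | 0.125 |
| 0.70 | 0.40 | 0.28 | −0.42 | 0.114 |

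At 80% capture the bias is below the half-width for p = 0.30 and 0.50, and slightly above it for p = 0.70. At 60% or less it exceeds the half-width in every row. A confidence interval would not reveal it.

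**The case against.** The strongest reply is that capture is better than the visit spacing suggests. AEs are sought on Day 0 by examination as well as by questioning, and section 14.3 asks for a start time for treatment-day events. Pain is rated twice per injection session, with scores of 4 or more recorded as AEs. Immediate redness, swelling, bleeding and pain can therefore be recorded, and the same holds on a touch-up day. Bruising may last longer than 1-2 days. Subjects are told to make contact between visits. All of this stands. A reader might infer that the common reactions are first asked about two weeks after injection, or that the schedule cannot measure them at all. The documents support neither reading.

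A reader might also infer that these reactions will make up most of the safety endpoint. Section 4.2 reports that 22 of 38 spontaneous reports (57.9%) for the same filler without lidocaine were of this kind, and section 3.2 describes short-term injection-site reactions in its 48-subject study. That makes the inference reasonable, but spontaneous reports are not incidence, and nothing is stated for this trial. The same experience tempers the statement that there are no human data on the present device.

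Finally, open questioning is a deliberate choice to avoid bias, and section 6.4.7 aims to avoid over-reporting of pain. That is a sound reason to put the open question first. It does not supply a record for the days after the subject leaves. A solicited list also has to be reconciled with the rule in section 6.4.7 on when pain counts as an AE.

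**Conclusion.** The point holds as probable under-ascertainment of unknown size. It affects the frequency, duration and peak severity of reactions that start or peak after the subject leaves on an injection day. The gaps of 12-16 days after Day 0 and 8-20 days after a touch-up follow directly from the visit windows, and the 1-2 day duration (bruising excepted) is the protocol's own.

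The direction of the bias rests on a judgement: that some subjects will neither call about a mild, expected reaction nor mention it at the next visit. That is plausible, but the documents do not quantify it. The table above shows only that under-capture could match or exceed sampling error.

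It would go too far to say that the safety objective is left unanswered for these events, because Day 0 collection, between-visit contact and the later visits all give some capture. No sample-size figure changes. This is an inexpensive improvement worth making.

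**What to change.** After Day 0 and after any touch-up, give each subject a one-page diary listing the reactions in the Common column of Table 2, with presence or absence, severity, and first and last day. Let it run for 14 days, or to the next visit if that comes sooner, since Week 2 can fall on day 12 and Week 4 can come 8 days after a touch-up. Collect it at Weeks 2 and 4.

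As a minimum, at those two visits ask the open question first, then go through the same list and record onset, end date and severity. This keeps the non-leading approach of section 14.2.

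In SAP section 4.5, tabulate the solicited reactions (rate, severity, duration) separately from the general AE table, so that the general table stays comparable. State whether and how a solicited reaction also enters that table, and how a diary entry for pain relates to the recording rule in protocol section 6.4.7. If the sponsor makes neither change, the report should label these rates as spontaneously reported or recalled.

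The cost is a paper form, one CRF page and one table, with no extra visit or staff. The downsides are a small burden on subjects and higher reported rates of mild, expected reactions.

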14.3 AE/SAE documentation

For each AE the following must be reported:

- description of the event (event term)
- start date
- start time (for events occurring on the treatment day)
- outcome
- end date (if applicable)
- severity
- action taken (none, medical and/or surgical)

- the relationship to the investigational device, the relationship to the procedure
- seriousness criteria.

The investigator will attempt to establish a diagnosis of the event based on signs, symptoms, and/or other clinical information. In such cases, the diagnosis will be documented as the AE/SAE and not the individual signs/symptoms.

Each AE should be reported separately. The investigator will record all AEs on the "AE" page of the CRF. For SAEs, the Serious Adverse Event Form must also be completed. Complete description of all AEs should be also available in the source documents.

AEs occurring after provision of informed consent and prior to application of the investigational medical device will be recorded as part of the medical history. Any medical condition that is present at screening should also be considered as medical history and not recorded as an AE. However, if the condition deteriorates after administration of the investigational device, at any time during the course of the investigation, it should be recorded and reported as an AE.

If the severity or seriousness of an AE changes over time, the most severe intensity or seriousness of the AE will be recorded and included in the analysis. No separate AEs will be recorded for each intensity level.

Changes in the assessment of the relationship to the investigational medical device or procedure should also be clearly documented.

Any medication necessary for the treatment of an AE must be recorded on the "Concomitant Medication" page of the CRF.

14.4 AE/SAE assessment

All AEs will be assessed in terms of:

- seriousness (yes, no)
- severity
- relationship to the investigational medical device or study procedures
- outcome.

14.4.1 Severity assessment

The severity of an AE/SAE will be graded as follows:

Mild: The AE is easily tolerated and does not interfere with daily activity

Moderate: The AE interferes with daily activity but the subject is still able to function

Severe: The AE is incapacitating and/or requires medical intervention

14.4.2 Causality assessment

The investigator is obligated to estimate the relationship between each AE/SAE and the investigational medicinal device or study procedure. Clinical judgement should be used and the relevant documents like IB consulted. The presence of confounding factors, such as concomitant medication/treatment, the natural history of the underlying disease, other concurrent illness or risk factors shall also be considered. The relationship should be determined using one of the following causality levels²⁰:

Definite: The AE/SAE is associated with the investigational device or with procedures beyond reasonable doubt when it is a known side effect of the product category the device belongs to, or of similar devices and procedures; has a temporal relationship with investigational device use/application or procedures; involves a body-site or organ that the investigational device or procedures are applied to or have an effect on; follows a known response pattern to the medical device application (or reduction of the level of exposure), when clinically feasible, and reintroduction of its use (or increase of the level of exposure) impact on the event; other possible causes (e.g. an underlying or concurrent

illness/clinical condition or/and an effect of another device, drug or treatment) have been adequately ruled out; and/or harm to the subject is due to error in use.

- **Probable:** The relationship with the use of the investigational device seems relevant and/or the event cannot be reasonably explained by another cause, but additional information may be obtained.
- **Possible:** The relationship with the use of the investigational device is weak but cannot be ruled out completely. Alternative causes are also possible (e.g. an underlying or concurrent illness/ clinical condition or/and an effect of another device, drug or treatment). Cases where relatedness cannot be assessed, or no information has been obtained, should also be classified as possible.
- **Unlikely:** The relationship with the use of the device seems not relevant and/or the event can be reasonably explained by another cause, but additional information may be obtained.
- **Not related**: Relationship to the device or procedures can be excluded when the AE/SAE is not a known side effect of the product category the device belongs to or of similar devices and procedures; has no temporal relationship with the use of the investigational device or the procedures; does not follow a known response pattern to the medical device (if the response pattern is previously known) and is biologically implausible; the discontinuation of medical device application or the reduction of the level of exposure, when clinically feasible, and reintroduction of its use (or increase of the level of exposure) do not impact on the event; involves a body-site or an organ not expected to be affected by the device or procedure; can be attributed to another cause (e.g. an underlying or concurrent illness/ clinical condition, an effect of another device, drug, treatment or other risk factors); and/or harm to the subject are not clearly due to use error.
- 14.4.3 Outcome assessment

The outcome of an AE will be assessed as follows:

Resolved:	The subject has fully recovered from the event, or the condition has returned to the level observed at baseline.
Ongoing:	The event is ongoing at the time of reporting and the subject has still not recovered.
Resolved with sequelae:	As a result of the AE, the subject suffered persistent and significant disability/ incapacity (e.g. became blind, deaf or paralyzed).
Fatal:	The subject died due to the event.
Unknown:	If outcome is not known or not reported.

